10.6.2.1 Impact on the Primary Endpoint of COVID-19 related study disruptions

To assess the impact on the primary efficacy results of COVID-19 related study disruptions (e.g. treatment discontinuation, missing assessments, remote visits, etc.), the following sensitivity analysis will be conducted:

1. The primary endpoint will be analyzed using a logistic regression model with treatment, analysis center and occurrence flag of COVID-19 related study disruptions impacting efficacy results as fixed effects. All subjects on the ITT population with missing data for the primary endpoint will be classified as non-responders regardless of treatment allocation (see section 10.6.4.2).
2. The primary endpoint will be analyzed using a logistic regression model with treatment, analysis center, occurrence flag of COVID-19 related study disruptions impacting efficacy results and interaction of treatment and occurrence flag of COVID-19 related study disruptions impacting efficacy results as fixed effects. All subjects on the ITT population with missing data for the primary endpoint will be classified as non-responders regardless of treatment allocation (see section 10.6.4.2). The interaction of treatment and occurrence flag of COVID-19 related study disruptions impacting efficacy results will be deemed statistically significant if the p-value for the interaction term is lower than 0.1 and, in this case, the primary analysis will be repeated separately in the two subgroups of subjects affected and not affected by COVID-19 related study disruptions impacting efficacy results.

10.6.2.2 Impact on the Primary Endpoint of subjects of Site PPD

Site PPD ([name]) was non-responsive. This prevented Source Data Verification from being performed. The eCRFs of subjects screened and randomized at this site were not signed by the investigator and queries were not answered. Data cannot be verified and queried.

To assess the impact of subjects of Site PP on the primary efficacy results, a sensitivity analysis for the primary endpoint will be performed on the ITT population by repeating the primary analysis with the exclusion of subjects randomized at this site.

10.6.3 Analysis of Secondary Endpoints

The hypothesis tests for the secondary endpoints can be formally defined as follows:

Statistical Analysis Plan

$$\begin{cases} H_0: \mu_{MAL} = \mu_{vehicle} \\ H_a: \mu_{MAL} \neq \mu_{vehicle} \end{cases}$$

where μ_{MAL} is the mean percent reduction from baseline in the number of cleared treated lesions at 12 weeks after the last MAL DL-PDT treatment (Visit 6) and $\mu_{vehicle}$ is the mean percent reduction from baseline in the number of cleared treated lesions at 12 weeks after the last vehicle DL-PDT treatment (Visit 6) and

$$\begin{cases} H_0: \pi_{MAL} = \pi_{vehicle} \\ H_a: \pi_{MAL} \neq \pi_{vehicle} \end{cases}$$

where π_{MAL} is the proportion of subjects with 75% or greater reduction from baseline in the number of cleared treated lesions at 12 weeks after the last MAL DL-PDT treatment (Visit 6) and $\pi_{vehicle}$ is the proportion of subjects with 75% or greater reduction from baseline in the number of cleared treated lesions at 12 weeks after the last vehicle DL-PDT treatment (Visit 6).

The hypothesis tests for the secondary endpoints will be evaluated on the ITT population at the two-sided significance level $\alpha = 0.00125$. The adjustment for multiple comparisons is described in section 10.6.4.5.

The number of cleared treated lesions at each analysis visit, the reduction from baseline and the percent reduction from baseline in the number of cleared treated lesions at each post-baseline analysis visit will be summarized descriptively by treatment groups (overall and by analysis centers). The percent reduction from baseline in the number of cleared treated lesions at 12 weeks after the last DL-PDT treatment (Visit 6) will be analyzed using an ANCOVA with treatment, analysis center (see definition in section 10.6.4.4) and baseline AK lesion count as fixed effects; the difference in percent reduction between MAL DL-PDT and vehicle DL-PDT, the 99.875% and 95% confidence intervals of the difference and the p-value will be generated from the ANCOVA model.

For analysis of percent reduction from baseline in the number of cleared treated lesions at 12 weeks after the last DL-PDT treatment (Visit 6), missing counts of lesions will be imputed using MI (Multiple Imputation) under the Missing At Random (MAR) assumption. It is expected that the pattern of missing data will be monotonic, with slight deviations being corrected by the Markov Chain Monte Carlo (MCMC) method of the MI procedure. Linear regression will be employed to model the missing lesion count data, with the following covariates included in the imputation model: treatment and non-missing data from earlier time points (see section 10.6.4.2).

Line plots will be produced over time for each treatment group to summarize the mean percent reduction from baseline in the number of cleared treated lesions.

The proportion of subjects with 75% or greater reduction from baseline in the number of cleared treated lesions at each post-baseline will be summarized descriptively by treatment groups (overall and by analysis centers). The proportion of subjects with 75% or greater reduction from baseline in the number of cleared treated lesions at 12 weeks after the last DL-PDT treatment (Visit 6) will be analyzed using the Cochran-Mantel-Haenszel (CMH) test stratified by analysis center (see definition in section 10.6.4.4). No continuity correction will be used. The p-value for the treatment comparison (MAL DL-PDT vs. vehicle DL-PDT) will be calculated from the general association statistic of the stratified CMH test. Difference in proportions between treatment groups and the 99.875% and 95% confidence intervals of the difference will be based on the large sample approximation method for binary data and will be calculated using the method described in the Huiping Zhang "Proportion difference and confidence interval based on Cochran-Mantel-Haenszel method in stratified multi-center clinical trial", 2016, PharmaSUG China 2016, Paper 25 [1]. In addition, the proportion of subjects with 75% or greater reduction from baseline in the number of cleared treated lesions at 12 weeks after the last DL-PDT treatment (Visit 6) for each treatment group will also be presented.

For the analysis of proportion of subjects with 75% or greater reduction from baseline in the number of cleared treated lesions at 12 weeks after the last DL-PDT treatment (Visit 6), all subjects of the ITT population with missing data will be classified as non-responders regardless of treatment allocation (see section 10.6.4.2).

Statistical Analysis Plan

A bar chart and line plots will be produced over time for each treatment group to summarize the partial responders.

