### 10.1.3.3 Secondary Endpoints Analysis

The percent reduction from baseline in the number of cleared treated lesions at 12 weeks after the last DL-PDT treatment (Visit 6) will be analyzed using an ANCOVA with treatment, analysis center and baseline AKs count as fixed effects; the difference in percent reduction between MAL DL-PDT and vehicle DL-PDT, the 99.875% confidence interval of the difference and the p-value will be generated from the ANCOVA model.

For analysis of percent reduction from baseline in the number of treated AK lesions, missing counts of cleared treated lesions for subjects on the ITT population will be imputed using MI (Multiple Imputation) under the Missing At Random (MAR) assumption. It is expected that the pattern of

---

missing data will be monotonic, with slight deviations being corrected by the Markov Chain Monte Carlo (MCMC) method of the MI procedure. Linear regression will be employed to model the missing lesion count data, with the following covariates included in the imputation model: treatment and non-missing data from earlier time points.

The proportion of subjects with 75% or greater reduction from baseline in the number of cleared treated lesions at 12 weeks after the last DL-PDT treatment (Visit 6) will be analyzed using the Cochran-Mantel-Haenszel (CMH) test stratified by analysis center. The p-value for the treatment comparison (MAL DL-PDT vs. vehicle DL-PDT) will be calculated from the general association statistic of the stratified CMH test. Difference in proportions between treatment groups and the 99.875% confidence interval of the difference will be based on the large sample approximation method for binary data.

For the analysis of proportion of subjects achieving a partial response, all subjects of the ITT population with missing data will be classified as non-responders regardless of treatment allocation.

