Approximately 675 subjects will be screened for a total of 570 subjects to be randomized (380 in the MAL DL-PDT arm and 190 in the vehicle DL-PDT arm using a 2:1 randomization ratio) to have approximately 100 subjects of MAL DL-PDT arm complete the long-term follow-up study, who had complete response for the primary endpoint. Randomization is stratified by study centers using the Interactive Response Technology (IRT) System.

Approximately 60 study centers are planned in the United States with approximately 8 subjects enrolled per center.

All attempts will be made to keep the study center staff and subjects blinded throughout the study. Members of the study center staff, including the procedure operator, will not have access to the randomized treatment assignment.

To ensure double-blind administration of study drug the study center pharmacist(s) or other qualified personnel will prepare all MAL 16.8% cream or vehicle cream treatments, according to the current version of the pharmacy manual provided by the IRT system.

[figure not shown]
The randomization code will remain blinded to all study centers and study team members until completion of the study and after the lock of the study database.

Personnel from Sponsor, CRO, and investigational centers directly involved with the ongoing conduct of the long-term follow-up study will not have access to any information that may lead to unblinding for the ongoing maintenance evaluation.

Statistical Analysis Plan

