9 SAMPLE SIZE CONSIDERATION

A long-term follow up study is planned to gather data about recurrences at around the 1 year time point after the DL-PDT treatments.

Subjects who achieve a complete response at Visit 6, 12 weeks after the last DL-PDT treatment, will be offered the opportunity to be followed in a 9-month long-term follow-up study to have treated lesions assessed for recurrence. The sample size calculation is based on providing enough subjects to enable the detection of a treatment difference in the primary endpoint and ensuring approximately 100 subjects of MAL DL-PDT arm complete the long-term follow-up study, who had complete response for the primary endpoint.

Approximately 675 subjects will be screened for a total of 570 subjects to be randomized (380 in the MAL DL-PDT arm and 190 in the vehicle cream DL-PDT arm using a 2:1 randomization ratio) to have approximately 100 subjects of MAL DL-PDT arm complete the long-term follow-up study, who had complete response for the primary endpoint. This study will have more than 90% power to detect a 30% difference between MAL DL-PDT (45% complete response rate) and vehicle DL-PDT (15% complete response rate) and with a type I error of 0.00125 assuming 7% subjects will be non-evaluable at 12 weeks after the last DL-PDT for the primary endpoint, 70% of subjects achieving a complete response at 12 weeks after the last DL-PDT will be enrolled in the LT follow-up study and dropout rate of 10% during LT follow-up study.

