10.1.4 Descriptive Statistics

For the descriptive statistics, unless otherwise noted, the categorical variables will be summarized by frequency and percentage (n, %) for each response category, and the continuous variables will be summarized using standard descriptive statistics (n, mean, standard deviation, median, first and third quartile, min and max).

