 - a. For binary outcome, the results from the CMH analysis will be combined using the procedure by Rubin [2] and Li et al. [3] to produce a pooled CMH statistic and p-value. The differences in proportions and standard errors will be combined using the SAS PROC MIANALYZE. The resulting pooled difference and standard error will be used to produce the confidence interval based on the large-sample approximation method for binary data without using continuity correction. Both these methods will be used as described in the Bohdana Ratitch, et al. "Combining Analysis Results from Multiply Imputed Categorical Data", 2013, PharmaSUG Proceedings, Paper SP-03 [4].

Statistical Analysis Plan

- b. For AK lesion count, results from the ANCOVA analysis will be combined using the SAS PROC MIANALYZE.

The number of fifty (50) imputations was selected in order to prevent a power falloff due to choosing a number of imputations too small [5].

As additional sensitivity analysis of the primary endpoint, the multiple imputation process for complete response binary outcome will be repeated based on the Pattern-Mixture Model under the missing not at random (MNAR) assumption, by using the profiles from vehicle DL-PDT subjects with observed data to impute missing data. The process will be the same described for the MAR analysis, only the assumption about missing mechanism will be changed.

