11 CHANGES FROM THE PROTOCOL ANALYSIS PLAN

Any change from the protocol will be justified and fully documented.

If the blind review suggests changes to the principal features stated in the protocol, these have to be documented in a protocol amendment. Otherwise, it will suffice to update the statistical analysis plan with the considerations suggested from the blind review.

Statistical Analysis Plan**12 SHELLS OF TABLES, FIGURES AND LISTINGS AND REPORTING OUTPUT (GENERAL FEATURES)**

Tables, figures and listings will be generated using SAS® and will be displayed on A4 size paper with landscape orientation, 2 cm for top and bottom margins, 0.8 cm for left and right margins and 8pt Courier New font.

The header section will comprise the sponsor's name, the protocol number, the delivery description, the TFL number, the TFL title, the population and the page number (Page X of Y). The footer section will include the TFL footnotes, the data extract date (if applicable), the date and time of the execution of the program, and the name of the program.

A clear, accurate and complete programming code will be developed to generate the statistical analyses, summary tables, figures and listings to be integrated in the report. Fluent use of precise titles and footnotes will be made to improve the understanding of summaries and document any assumption. Details of analysis specifications including but not limited to the SAS code will be documented on the shells.

Statistical Analysis Plan

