13 APPENDICES

13.1 Shells for Table, Figure and Listings

The final list of tables, figures and listings and their shells for the reporting of this study will be available in a separate document that will be developed and will be finalized before database lock.

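### Both confidence intervals for percent lesion reduction come from an ANCOVA that, as ordinarily read, uses one residual variance under 2:1 allocation; they miss their stated coverage if the arm SDs differ, in a direction the documents do not fix

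*SAP*

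**What the plan says.** SAP 10.6.3 analyses percent lesion reduction at Visit 6 with treatment, analysis center and "baseline AK lesion count as fixed effects; the difference in percent reduction between MAL DL-PDT and vehicle DL-PDT, the 99.875% and 95% confidence intervals", and takes the p-value from the same model. Protocol 10.1.3.3 has the same model with one interval: "the 99.875% confidence interval of the difference and the p-value will be generated from the ANCOVA model". SAP 10.1.5 states the nominal coverage of both intervals as two-sided 99.875% and 95%.

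Missing counts are multiply imputed, each of the 50 completed datasets is analysed as in 10.6.3 (step 3 of 10.6.4.2), and step 4 pools the results: "For AK lesion count, results from the ANCOVA analysis will be combined using the SAS PROC MIANALYZE".

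SAP section 4 gives the allocation: "380 in the MAL DL-PDT arm and 190 in the vehicle DL-PDT arm using a 2:1 randomization ratio". SAP 10.6.4.5 tests this endpoint immediately after the primary, at 0.00125.

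Neither document names a residual variance structure, a robust SE or a sensitivity analysis for this endpoint; the sensitivity analyses in SAP 10.6.2 concern the primary endpoint only. SAP section 12 leaves the code to the shells ("Details of analysis specifications including but not limited to the SAS code will be documented on the shells"), which, under 13.1, "will be available in a separate document that will be developed and will be finalized before database lock".

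**The concern.** An ANCOVA specified only by its fixed effects is ordinarily fitted with a single residual variance. Under equal allocation, unequal arm variances would not matter for the treatment difference. Under 2:1 they do: the larger MAL arm dominates the pooled variance, while the smaller vehicle arm dominates the true variance of the difference. If vehicle responses are more variable, the intervals are too narrow; if MAL responses are more variable, they are too wide.

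Equal SDs cannot be taken for granted. The outcome is a bounded percentage, and the plan expects very different responses in the two arms (45% and 15% complete response).

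At stake is the reported precision of one gated secondary estimate. That interval will be read, because SAP 10.6.1 makes the single-study efficacy claim depend partly on consistency between primary and secondary endpoints.

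**Working it through.** **The plan's own figures.** None concerns this endpoint: no SD, power or sample size is given for percent reduction. SAP section 9 sizes the trial on the primary endpoint (45% vs 15%, alpha 0.00125, "assuming 7% subjects will be non-evaluable at 12 weeks after the last DL-PDT for the primary endpoint"). Its figures reproduce: power with 7% removed is 99.999%, above the stated 90%, and 380 × 0.93 × 0.45 × 0.70 × 0.90 = 100.2 MAL long-term completers. Neither figure fixes the arm SDs.

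**Variance of the difference.** Let the arms have 2n (MAL) and n (vehicle) subjects, with residual SDs σ and rσ.

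- True variance: σ²/(2n) + r²σ²/n = σ²(1 + 2r²)/(2n).
- Expected pooled variance: σ²(2 + r²)/3. Model variance: that × (1/(2n) + 1/n) = σ²(2 + r²)/(2n).
- True / model = (1 + 2r²)/(2 + r²).

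The ratio is 1 only at r = 1 and does not contain n. At 1:1 allocation it would be 1 for every r. Losing 7% from each arm does not alter it.

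**Coverage.** Coverage = 2Φ(z·k) − 1, with k = √[(2 + r²)/(1 + 2r²)] and z = 1.960 or 3.227. For r = 1.5: k = √(4.25/5.5) = 0.879, z·k = 1.723, coverage 91.5%.

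| r | 95% CI covers | 99.875% CI covers |
|---|---|---|
| 0.7 | 97.2% | 99.97% |
| 0.8 | 96.5% | 99.95% |
| 1.0 | 95.0% | 99.875% |
| 1.25 | 93.1% | 99.73% |
| 1.5 | 91.5% | 99.54% |
| 1.8 | 89.9% | 99.31% |

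**Which r are possible (assumption).** Take beta-binomial clearance with 4 to 12 lesions equally likely, and solve each arm's mean to give 45% and 15% complete response. The within-subject correlation is not in the documents.

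- Common correlation 0.05: SDs 0.137 (MAL) and 0.190 (vehicle), r = 1.38, coverage 92.2%.
- Common correlation 0.7: SDs 0.416 and 0.391, r = 0.94, coverage 95.5%.
- MAL 0.4, vehicle 0.2: r = 0.91, coverage 95.7%.
- MAL 0.2, vehicle 0.5 (a stress case): r = 1.80, coverage 89.9%.

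Using instead the 70.1% MAL mean from the European study in Protocol 6.2.1 (one session, PP population), with vehicle means assumed at 25–60%, gives r = 0.81–1.09 and coverage 94.3–96.4%.

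**Simulation of the planned procedure.** 570 subjects in 38 centers of 15 (10:5), 7% missing at random, 50 imputations by linear regression, ANCOVA, Rubin pooling; 8,000 trials per setting (Monte Carlo error about ±0.5 points on 95% coverage). Visit 4 clearance was assumed to be half the final probability.

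| Setting | 95% coverage, pooled / arm-specific | Misses of 99.875% CI (10 expected) | Rejection at 0.00125 |
|---|---|---|---|
| 45%/15%, correlation 0.05 in both | 92.1 / 94.5 | 26 / 9 | 100% / 100% |
| 45%/15%, 0.7 in both | 95.4 / 95.0 | 3 / 6 | 100% / 100% |
| 45%/15%, MAL 0.4, vehicle 0.2 | 95.6 / 95.0 | 7 / 13 | 96.7% / 97.5% |
| 45%/15%, MAL 0.2, vehicle 0.5 | 89.9 / 94.5 | 63 / 10 | 100% / 100% |
| Means 70.1% / 60% (assumed small effect) | 96.7 / 95.3 | 2 / 9 | 49.7% / 58.3% |

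The pooled results follow the formula. Multiple imputation does not repair them, because the within-imputation variance is the ANCOVA variance itself.

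**Type I error.** With no effect and identical arms, 8,000 trials gave 12 rejections (pooled) and 13 (arm-specific) against 10 expected. The null in SAP 10.6.3 is equality of means, however. With equal means and unequal SDs, the error is one minus the coverage above: about 0.0005 at r = 0.8, 0.0027 at 1.25 and 0.0046 at 1.5.

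**The case against.** The strongest reply is that nothing here contradicts the plan. ANCOVA with treatment, center and baseline is a conventional prespecification, the variance structure is inferred, and the code sits in shells that may already allow for unequal variances. The low coverage figures need assumed correlations, and anchoring on the 70.1% lesion figure keeps coverage near nominal. The spread by arm will also be visible, since under SAP 10.1.4 "the continuous variables will be summarized using standard descriptive statistics (n, mean, standard deviation, median, first and third quartile, min and max".

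Much of this stands. It limits the point to a condition and keeps it at low severity. It does not remove it: the documents leave the variance assumption unstated, tabulated SDs do not correct an interval, and no planned output does.

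A reader might go further and infer three things that the documents do not support:

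- **That the intervals are too narrow.** No arm SD is given, and r can fall on either side of 1 at the stated response rates.
- **That the gated test has an inflated type I error.** If the arms have the same variance, for example identical distributions, the level holds. With equal means and unequal SDs it departs from 0.00125, but it may be lower or higher.
- **That the efficacy claim is at risk.** The claim is tested by the primary CMH analysis, which does not use this variance, and neither does the partial-response CMH analysis.

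**Conclusion.** The point holds conditionally. If the ANCOVA pools one residual variance and the arm SDs differ, the 95% and 99.875% intervals for percent lesion reduction do not have their stated coverage, whatever the sample size. The formula is normal-theory and treats r as the ratio of residual SDs.

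Size and direction are unknown. With a common assumed correlation of 0.05–0.7 at the stated 45%/15% rates, coverage of the 95% interval is 92.2–95.5%; arm correlations that differ widen that range in both directions.

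The decision at this step of the hierarchy barely moves at the planned effect: the largest change in the settings calibrated to 45%/15% was 96.7% versus 97.5%. A larger change appeared only under an assumed small effect. Severity is low: a cheap improvement to one secondary interval, not an error that endangers the trial's conclusion.

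**What to change.** Before unblinding, state in SAP 10.6.3 and in step 3 of 10.6.4.2 that the same ANCOVA fixed effects are fitted within each imputed dataset with arm-specific residual variances (for example PROC MIXED with REPEATED / GROUP=treatment and Satterthwaite degrees of freedom), or with a heteroscedasticity-consistent SE, before the MIANALYZE pooling. The imputation model can stay as planned. Record this under SAP section 11 as a clarification or a justified change, and carry it into the shells before database lock. At minimum, add it as a prespecified sensitivity analysis. If the shells already specify unequal variances, saying so in 10.6.3 is enough.

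The cost is a sentence in each of the two places, a line of code and the section 11 record. The downside is that the interval may widen or narrow. In the simulations the arm-specific SE was 10% and 18% larger where r > 1 (1.59 vs 1.44 and 2.94 vs 2.49 percentage points) and 2–6% smaller where r < 1 (3.58 vs 3.65, 2.53 vs 2.59, 2.86 vs 3.04).
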